#### Analysis

- Immunogenicity will be assessed through summary tables, figures, and listing of individual results by subject. The analysis of immunogenicity will be summarized by treatment sequence as described in Section 9 and visit. All analyses will be run on the safety population, unless specified otherwise. Summary of anti-bimekizumab antibody status overall and by each visit separated by treatment sequence
- Summary of the time-point of the first occurrence of anti-bimekizumab antibody positivity during the treatment period by treatment sequence. A plot of the titer by time to first anti-bimekizumab antibody positivity will be prepared
- All individual subject-level anti-bimekizumab antibody results will be listed.
- The number and percentage of subjects in each of the 8 anti-bimekizumab antibody categories during the treatment period by treatment sequence, with an additional category combining subjects in categories 2 and 5, summarized as total treatment emergent. In addition, the count and percentage of subjects who are pre anti-bimekizumab positive will be calculated (this is the sum of categories 3, 4, and 5)
- The prevalence of immunogenicity, separated by treatment sequence, and defined subcategory, will be reported by visit, defined as (cumulative) proportion of subjects having confirmed positive anti-bimekizumab antibody samples at any visit up to and including that visit. Missing samples will not be included in the denominator
- The time to achieving treatment-emergent anti-bimekizumab antibody positivity, separated by treatment sequence and defined sub-category, will be analyzed based on Kaplan-Meier methods. Subjects will be considered to have an event at the time point at which treatment emergent anti-bimekizumab antibody positive is first achieved. Subjects classified as treatment-emergent anti-bimekizumab antibody negative will be censored at the time of the last available anti-bimekizumab antibody result

- A summary of PASI 100 responders, separated by treatment sequence and defined sub-category, at weeks 16, 48 and 144 as a function of ADA b titer will be presented graphically. This will be repeated for PASI 75 and 90 responders
- Individual plots of Bimekizumab Concentrations/ anti-bimekizumab antibody titer and PASI score all plotted on the Y-axis by visit (x-axis) for the full treatment period (excluding SFU and OLE period for interim analyses and including SFU and OLE period for final analyses), where a patient has not progressed into the OLE. Plots should be labeled and grouped into the 7 sub-categories
- Spaghetti plots of ADA b titer (y-axis) by visit (x-axis), separated by treatment sequence (as specified above) for all anti-bimekizumab antibody positive subjects, including Baseline positive subjects
- Box plots Plot of ADA b titer (logscale) by time to first ADA b positivity by treatment sequence.

For purposes of efficacy subgroup analyses based on anti-bimekizumab antibody status, two categories will be used:

- Anti-bimekizumab antibody positive – This is defined as subjects who have anti-bimekizumab antibody levels above the specified cut point on at least 2 time points while on treatment (ie, excluding Baseline, excluding SFU)
- Anti-bimekizumab antibody negative – Subjects who are not defined as anti-bimekizumab antibody positive (as described above) will be defined as anti-bimekizumab antibody negative.

The groups for defining anti-bimekizumab antibody status for safety subgroup analyses are as follows:

- AEs starting before first anti-bimekizumab antibody positive result
- AEs starting on or after first anti-bimekizumab antibody positive result
- AEs for subjects who were always anti-bimekizumab antibody negative.

In addition to the anti-bimekizumab antibody classifications, subjects will be assigned an overall neutralizing anti-BKZ antibodies (NAb) classification for each NAb assay separately (IL-17AA and IL-17FF), inclusive of Baseline and post-Baseline results, on the NAb assay results. The classifications are as follows:

- NAb negative: No NAb positive samples at Baseline or post-Baseline and did not discontinue prior to Week 144. Subject can have up to 1 missing sample.
- NAb positive: One or more positive samples (IL-17AA positive, IL-17FF positive, or both) at Baseline or post-Baseline (regardless of missing samples). Subjects who are NAb positive will be further classified as follows:
  - Positive for IL-17AA only: one or more positive samples for IL-17AA at Baseline or post Baseline. No positive samples for IL-17FF
  - Positive for IL-17FF only: one or more positive samples for IL-17 FF at Baseline or post Baseline. No positive samples for IL-17AA

- Positive for both IL-17AA and IL-17FF: one or more positive samples for both IL-17AA and IL-17FF at Baseline or post Baseline
- NAb Missing: >1 relevant NAb samples are missing, eg, if subject had samples selected for NAb testing based on their anti-bimekizumab antibody levels, but there was insufficient sample left for NAb testing.

A summary table covering the initial, maintenance and OLE periods combined by treatment sequence will be produced, in addition, to summarize the NAb status overall.

A listing will be produced to summarize the NAb status by visit. The listing should be sorted by treatment sequence, subject identifier, and visit and would provide the following information for each subject:

- Visit
  - Study week since first BKZ dose
  - Sample date and time
  - Time since previous dose (weeks)
- NAb status and the corresponding bimekizumab plasma concentration (ug/mL) and the anti-bimekizumab antibody level titer at this visit
- IL-17AA NAb status and corresponding IL-17AA signal/negative control result  
IL-17FF NAb status and corresponding IL-17FF signal/negative control result

The tables will provide the following overall summary statistics by treatment group:

- Total number and percentage of anti-bimekizumab antibody positive, anti-bimekizumab antibody negative and missing subjects at each visit
- Number and percentage of subjects who are NAb positive, NAb negative and missing at each visit
- The number and percentage of subjects who are IL-17AA NAb positive, IL-17FF NAb positive, or both.

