#### **4.8 Examination of subgroups**

Subgroup analyses will be based on data up to Week 48 only. These analyses will be performed on the PASI75/90/100 response rates, using by visit summaries only. The following subgroups for analysis will be determined for the RS using baseline data:

- Age (<40 years, 40 to <65 years, ≥65 years)
- Gender (male, female)
- Disease duration (<median, ≥median)
- Region (North America, Western Europe, Central/Eastern Europe, Asia/Australia)
- Weight (≤100 kg, >100 kg)
- Body mass index (BMI) (<25 kg/m^2, 25 to <30 kg/m^2, ≥30 kg/m^2)
- Prior systemic phototherapy or chemotherapy (yes, no)
- Prior biologic exposure (yes, no)
- Prior primary failure to biologic (yes/no)
- Prior systemic therapy of any kind (yes, no)
- Baseline disease severity (PASI<20, PASI≥20)
- Antibody positivity (negative, positive)

Antibody positivity is the only subgroup that is not determined by Baseline data (described in Section 9.3.2). It will be presented in a separate table.

The definition of prior systemic therapy of any kind is if a subject received previous biologic therapy, previous systemic therapy (non-biologic), or previous systemic chemotherapy or phototherapy. Subjects who never received previous biologic therapy, previous systemic therapy (non-biologic), or previous systemic chemotherapy or phototherapy will be classified as not receiving prior systemic treatment for psoriasis.

In addition, in order to assess whether an early response to treatment is predictive of response at later time points, subgroup analyses will be performed for PASI90/100 and IGA over time using the following early response subgroups:

- PASI75 response (OC) at Week 4 (yes, no) to predict PASI90/100 and IGA (clear or almost clear) (NRI) through Week 48 based on RS
- PASI90 response (OC) at Week 16 (yes, no) to predict PASI100 (NRI) through Week 48 based on RS
- PASI90 response (OC) at Week 48 (yes, no) to predict PASI90 (NRI) during the OLE based on OLS
- PASI90 response (OC) at Week 48 (yes, no) to predict PASI100 (NRI) during the OLE based on OLS
- PASI90 response (OC) at Week 48 (yes, no) to predict IGA responder rates (clear) and IGA responder (clear or almost clear) during the OLE based on OLS.

All summaries will be based on imputed data as appropriate and will include descriptive statistics only.

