### **8.3 Analysis of other efficacy variables**

The other efficacy variables are listed below and will be evaluated according to the planned assessments in the protocol. This excludes the time points for the primary and secondary variables specified above in Section 8.1.1.2 and Section 8.2.1.

Three different types of tables will be produced by visit through Week 48:

1. Subjects in the MS summarized by the 3 maintenance treatment groups (bimekizumab 320mg Q4W, bimekizumab 320mg Q8W, and secukinumab).
2. A subset of Group 1 above. Specifically, this will include only those subjects who are responders at Week 16 for the variable being summarized.
3. Subjects in the RS summarized by the 2 randomized treatment groups (bimekizumab and secukinumab).

All efficacy variables will be summarized in the manner described for Group 1 and Group 3 above. Summaries for Group 2 will be done only for a subset of efficacy variables, namely, PASI90/100 responder rate, IGA Clear or Almost Clear. Examination of subgroups will only be done for Group 3.

Binary (responder) variables will be summarized using frequency tables by treatment group for each visit. Continuous variables will be summarized using descriptive statistics by treatment group for each visit. All variables will be summarized based on imputed data (NRI and MCMC/Monotone Regression for binary and continuous variables, respectively), unless otherwise specified.

For variables that are part of the sequence testing procedure, summaries based on observed case data will also be provided. There may be cases where the multiple imputation model fails to converge. In such situations, the LOCF approach will instead be used to impute the missing data. Selected efficacy variables will also be summarized by visit through Week 144 for the OLE Period for the OLS. Subjects will be summarized by treatment sequence comprising randomized treatment at Baseline and OLE period treatment at Week 48.

The OC approach will be used to summarize the following efficacy variables for subjects in the OLE2 treatment period: PASI90, PASI100, IGA (0/1), IGA (0), DLQI (0/1), and PSD response.

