### 9.3.2 Anti-bimekizumab antibodies

Anti-bimekizumab antibodies will be measured using a three tiered assay approach: screening assay, confirmatory assay and titration assay. Samples confirmed as positive within the confirmatory assay, will be further evaluated in a neutralizing assay to evaluate the potential of the ADAb to neutralize the activity of Bimekizumab (IL17A or IL17F, or both) in-vitro. Samples were taken at baseline, week 1, week 2, week 4, week 8, week 12, week 16, week 20, week 24, week 36, week 48, Week 72, Week 96, Week 120, Week144 (or PEOT) and at SFU which is 20 weeks after the last dose. Due to the planned entry of some subjects to the OLE2 period, not all subjects will have an SFU period immediately following Week 144 with PK and immunogenicity samples.

Anti-bimekizumab antibody samples are not analyzed when subjects are on a treatment other than bimekizumab. For subjects who switch from secukinumab to bimekizumab, samples are analyzed starting at the visit when the switch to bimekizumab occurs. The sample at the visit when the switch occurs will act as the Baseline for that treatment group.

Screening, confirmatory and titer cut points of the respective assays will be determined by the bioanalytical laboratory based either on using commercially available drug-naïve samples or on the pre-dose samples of the study itself. The samples (or a subset) will also be subject to a neutralizing assay to evaluate whether the anti-bimekizumab antibody neutralizes the activity of bimekizumab (IL17 A or IL17F or both) in- vitro.

The following definitions will be applied regarding ADAb status of each test samples:

- An ADAb status will be confirmed as positive for any sample with an ADAb level that is positive screen and positive immunodepletion.
- An ADAb status of negative will be concluded for any sample with an ADAb level that is either negative screen or (positive screen and negative immunodepletion).

If the titer for an ADAb level that is positive screen and positive immunodepletion is missing, then a conservative approach will be used and ADAb status will be considered as positive. No imputation rules apply for the missing titer. If the ADAb level is positive screen but no confirmatory result could be determined, then a conservative approach will be used and ADAb status will be considered as positive.

Anomalous values will be not included in summaries/analysis and will be reviewed and flagged by pharmacokinetic expert.

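### The antibody-status efficacy subgroup, as written, places the whole untested secukinumab arm in the antibody-negative stratum; it should be restricted to subjects randomized to bimekizumab

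*SAP*

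**What the plan says.** Section 4.8 of the SAP sets out subgroup summaries of PASI75, PASI90 and PASI100 response by visit, on data up to Week 48. It introduces the list with "The following subgroups for analysis will be determined for the RS using baseline data". Antibody positivity (negative, positive) is on the list. Section 4.8 adds that this is the one subgroup not fixed at Baseline, gives it a table of its own, and sends the reader to Section 9.3.2 for the definition.

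Section 8.3 says which kind of table carries the subgroups. Of its three table types, Group 3 is the RS split by the two randomized arms, and "Examination of subgroups will only be done for Group 3".

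Section 9.3.2, under Analysis, defines two categories for efficacy subgroups. Positive means "subjects who have anti-bimekizumab antibody levels above the specified cut point on at least 2 time points while on treatment", with Baseline and SFU samples not counted. For everyone else the rule is: "Subjects who are not defined as anti-bimekizumab antibody positive (as described above) will be defined as anti-bimekizumab antibody negative". There is no category for subjects who were not tested.

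On which samples are assayed, Section 9.3.2 says: "Anti-bimekizumab antibody samples are not analyzed when subjects are on a treatment other than bimekizumab". It continues: "For subjects who switch from secukinumab to bimekizumab, samples are analyzed starting at the visit when the switch to bimekizumab occurs". The switch-visit sample then serves as Baseline for those subjects.

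**The concern.** Each rule is reasonable alone; the trouble comes from combining them. A two-arm table is stratified by a variable that is measured in only one arm, and the definition turns not measured into negative.

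Two consequences follow. The positive stratum has no secukinumab subjects, so it offers no comparison between arms. The negative stratum has bimekizumab subjects left after those with two or more positive samples are removed, next to secukinumab subjects from whom nobody has been removed. Antibody status arises after randomization and may be related to response, so randomization does not protect that comparison. A reader who sees two columns under an antibody-negative heading would naturally take it for a like-for-like comparison.

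What is at stake is the reading of a descriptive table. The useful question, whether response differs by antibody status among subjects given bimekizumab, needs only the bimekizumab column.

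**Working it through.** **Inputs.** Section 2.4 gives 350 subjects per arm and assumed Week 16 PASI100 rates of 60% (bimekizumab) and 44% (secukinumab). Section 9.3.2 gives the sampling times and the antibody definitions. Sections 4.8 and 8.3 give the population and the Week 48 limit. The SAP gives no antibody positivity rate and no response rate by antibody status.

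**The plan's own figure.** Section 2.4 states 98% power for superiority. With pooled variance under the null:

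- SE under the null = sqrt(2 × 0.52 × 0.48 / 350) = 0.0378
- SE under the alternative = sqrt((0.60 × 0.40 + 0.44 × 0.56) / 350) = 0.0373
- power = Φ((0.16 − 1.96 × 0.0378) / 0.0373) = 98.9%

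This agrees with the SAP to within a point. The design figures are not in dispute and serve below only as a base.

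**Step 1: apply the rules to a secukinumab subject.** The subject is in the RS, so Sections 4.8 and 8.3 put the subject in the table. No sample is analyzed while the subject is on secukinumab. Testing starts at the switch to bimekizumab, at Week 48 at the earliest, and that first sample is Baseline, which the definition of positive excludes. Leaving aside anyone given bimekizumab in error, no secukinumab subject can have two on-treatment positive samples by Week 48. The catch-all makes the subject negative.

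**Step 2: count the cells.** Let f be the proportion of bimekizumab subjects classed as positive. At planned size, bimekizumab has 350f positive and 350(1 − f) negative; secukinumab has 0 positive and 350 negative, whatever f is.

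**Step 3: what the negative stratum would show.** Let g be the number of points by which bimekizumab response is lower in positives than in negatives. Holding the overall bimekizumab rate at 60%:

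- 60 = (1 − f) × N + f × (N − g), so the negative-stratum rate is N = 60 + f × g
- the secukinumab rate stays at 44, because nobody has been removed
- the difference shown is 16 + f × g points

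Both f and g are assumptions.

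| f | Bimekizumab positive / negative | Secukinumab positive / negative | g = 0 | g = 10 | g = 20 |
|---|---|---|---|---|---|
| 10% | 35 / 315 | 0 / 350 | 16.0 | 17.0 | 18.0 |
| 20% | 70 / 280 | 0 / 350 | 16.0 | 18.0 | 20.0 |
| 30% | 105 / 245 | 0 / 350 | 16.0 | 19.0 | 22.0 |
| 45% | 157.5 / 192.5 | 0 / 350 | 16.0 | 20.5 | 25.0 |

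**Step 4: compare with the SAP's other outputs by antibody status.** Section 9.1 repeats the PK table and figures by cumulative antibody status only for subjects randomized to bimekizumab. Section 10.2.2 limits the adverse-event summary by onset relative to antibody status to bimekizumab-treated subjects. The efficacy subgroup carries no such limit. Nor do the analysis sets in Section 9.3 supply one: the Safety Set used for the Week 48 interim contains both arms, and the Bimekizumab Set includes secukinumab subjects once they receive bimekizumab in the OLE.

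**The case against.** **A bimekizumab-only table may be what was intended.** Section 4.8 gives this subgroup a separate table, the Week 48 groups in Section 9 are bimekizumab only, and the PK and adverse-event outputs by antibody status are restricted. This makes a two-arm table less than certain in practice. It does not settle the text: the separate table is mentioned next to the remark that status is not a Baseline variable, and Section 8.3 assigns subgroup examination to the two-arm Group 3.

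**The stakes are low.** Sections 4.2.1.4 and 4.8 limit subgroups to descriptive statistics, and they lie outside the fixed sequence in Section 4.5. An empty secukinumab cell in the positive stratum would also be visible to a reader. All of this stands.

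**Three stronger readings are tempting, and the SAP does not support them.**

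- A reader might infer that the secukinumab arm is wrongly classified. These subjects are untested, and a subject never given bimekizumab has no on-treatment exposure to induce such antibodies. The label is uninformative rather than shown to be false.
- A reader might infer that early leavers counted as negative substantially dilute the negative response rate. Samples at Weeks 1, 2 and 4 mean that very few subjects will have fewer than two. The SAP gives no leaver rate, and Section 4.2.1 expects few discontinuations before Week 16. Antibody-positive leavers also become non-responders under NRI, so the direction is not fixed either.
- A reader might want to import the two-thirds-evaluable rule from the overall status. Section 9.3.2 defines that rule up to Week 144 and says that it departs from the Week 48 interim, which had no missing class. With 10 post-Baseline samples to Week 48, it would require 7, so a tested-negative subject leaving before about Week 20 would drop out while a positive subject leaving at the same time stayed in as a non-responder. That would remove failures from one stratum only.

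**Conclusion.** The point holds on the wording of Sections 4.8, 8.3 and 9.3.2 read together. The secukinumab part follows from the rules alone: the entire arm, about 350 subjects at planned size, is labelled antibody negative without a test, and the positive stratum has no comparator. The negative-stratum display is therefore not a subgroup comparison.

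Its numerical effect cannot be derived from the SAP. Under the assumed ranges above, the difference shown would be 1 to 9 points larger than the planned 16; if antibodies do not affect response, there is no shift. No hypothesis test, alpha, power or sample size is touched. This is worth correcting because the stated rule produces a stratum without meaning and the remedy is nearly free.

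**What to change.** In Sections 4.8 and 9.3.2, state that the antibody-status efficacy subgroup is confined to subjects randomized to bimekizumab, as Sections 9.1 and 10.2.2 already do for PK and adverse events. Add the matching exception to the Group 3 sentence in Section 8.3. If secukinumab is shown at all, show it once as an unstratified reference column and not under an antibody heading.

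In Section 9.3.2, show bimekizumab subjects with no evaluable on-treatment antibody sample as not evaluable instead of negative, and print their number. Given the Week 1 sample this should be a very small group, so the removal of NRI non-responders from the negative stratum is kept to a minimum.

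The cost is a few lines of SAP text, a population filter and one extra row in one table. Table 12–3 provides for Week 48 analyses to be rerun at the Week 144 and final analyses, so the corrected table can be produced there.

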## 10 SAFETY ANALYSES

If not specified otherwise, all safety summaries and listings will be created using all subjects in the SS.

### 10.1 Extent of exposure

Summaries for exposure will be provided for the SS, MS, OLS, OLS2, and BKZ set. These consist of a descriptive summary of study medication duration in days. In addition, total study medication duration and time at risk will be summarized in years by treatment group

The cumulative study medication duration will be summarized for the SS for subjects exposed for given durations of time, the following categories for duration will be used:

- >0 weeks
- >=16 weeks

- $\geq 24$  weeks
- $\geq 48$  weeks

For the Week 144 analysis and for the final analysis, the table will also be created for the BKZ set and will include the above categories plus the below categories. A bimekizumab total column will also be displayed.

- $\geq 72$  weeks
- $\geq 96$  weeks
- $\geq 120$  weeks
- $\geq 144$  weeks

In addition, the OLE2 exposure will be displayed separately as follow:

- $> 0$  weeks
- $\geq 16$  weeks
- $\geq 24$  weeks
- $\geq 48$  weeks.

Definitions for study medication duration and time at risk in days are provided below. Time at risk will be summarized in years. Time at risk in years is calculated by dividing the time at risk in days by 365.25.

Throughout this section, date of last clinical contact for each subject is defined as the maximum of (last visit date including SFU or SFU2 visit, last imputed AE start date, date of study termination or completion, last date of study drug administration).

